2 GENERAL INFORMATION

2.1 Background details

All study data will be transferred to a SAS database (version 9.4 or later, SAS institute, North Carolina, USA) for statistical analysis purposes. Data will be imported from a Data Capture System IBM Inform via validated SAS programs.

The SAP will be finalized before the interim analysis, any changes needed after the DMC meeting will lead to an SAP amendment which needs to be finalized before database lock and unblinding after agreement with the Sponsor on subject disposition and coding.

Statistical Analysis Plan	Version 1.0		Page 8 of 25
Sponsor	MedinCell	Protocol No	mdc-TTG-CT-002

Deviations from the protocol will be judged during the study and/or when an individual participant's CRF is completed (monitored).

Before unblinding the data, a blinded data review meeting (BDRM) will take place where protocol deviations will be classified (major/minor protocol deviations) for statistical analysis. Intake of pain medications such as acetylsalicylic acid and metamizole, will not be considered a major protocol deviation.

2.3 Individual protocol deviations

Apart from violations of in- or exclusion criteria, no individual protocol deviations have been determined a priori.

A detailed review of all documented and derived deviations from protocol will be part of the blinded DRM before database lock. During this DRM the impact of protocol deviations on the analysis will be assessed and the conclusions recorded.

A complete listing of documented and derived protocol deviations and the judgment for assessment of subject disposition will be signed before database lock. A description of protocol violations that led to exclusion from any analysis sets will be included in the table part of the CSR.

3 ANALYSIS POPULATIONS

In general, the disposition of subjects will be displayed for the subject populations defined below.

Membership of subjects will be decided upon in a blind DRM with the Sponsor before database lock. The proper flag for analysis sets exclusion (e. g. exclusion from PP set), will be included in the analysis datasets. The protocol deviation list should be finalized before database lock.

3.1 Randomized Set

The randomized set includes all participants who were randomised.

3.2 Safety Set

The safety set (SS) includes all participants who received at least one tablet of the study drug (ivermectin or placebo).

Statistical Analysis Plan	Version 1.0		Page 9 of 25
Sponsor	MedinCell	Protocol No	mdc-TTG-CT-002

3.3 Full Analysis Set

The Full Analysis Set (FAS) includes all participants randomly assigned to a treatment group having received at least one tablet of the study drug (ivermectin or placebo) and having at least one efficacy assessment after randomisation.

3.4 Modified Full Analysis Set

Modified FAS (mFAS) includes all FAS participants with a confirmed negative SARS-CoV-2 RT-PCR test at baseline.

3.5 Per-protocol Set

The Per-Protocol Set (PPS) is a subset of participants in the mFAS who did not present major deviations from the trial protocol.

The primary efficacy endpoint will be analysed using the mFAS and the PP set. The PP analysis will be considered as a sensitivity analysis.

Secondary efficacy endpoints will be analysed using the FAS or mFAS and PP set.

In case of dispensation/randomisation major error (i.e. the participant did not receive the treatment planned by the randomisation), in agreement with the intention-to-treat (ITT) principle, participants in FAS and mFAS analyses will be analysed in the group planned by the randomisation and not "as treated". As treated analyses will be performed as sensitivity analyses only if the frequency of major dispensation/randomisation error is greater than 10%.

The safety set will be used for safety analyses. In case of dispensation/randomisation major error the safety analyses will be performed "as treated", according to the real treatment received by the participant.

4 STATISTICAL ANALYSES

All statistical analyses will be performed using the SAS® software (Version 9.4 or later, SAS institute, North Carolina, USA).

All descriptive statistics will be given by treatment group. For baseline and basic variables, they will also be given for the entire analysis set. Screening failure data will not be analysed.

If not stated otherwise the following standard types of descriptive analyses will be presented:

- Descriptive statistics for continuous data

Statistical Analysis Plan	Version 1.0		Page 10 of 25
Sponsor	MedinCell	Protocol No	mdc-TTG-CT-002

N, mean, SD, min, lower quartile, median, upper quartile, and max will be presented. These descriptive statistics will be determined for measured values and optionally for differences to baseline.

Descriptive statistics for categorical data

Absolute frequencies and percentages will be presented. Percentage bases (denominators) will be identified in the table title or footnote (i.e. all subjects at risk, all cases). For changes from baseline, shift tables may be generated.

Inferential statistics

Unless otherwise stated, all statistical tests will be performed two-sided and at a type I error probability of α =0.05.

Unless otherwise stated, all confidence intervals (CIs) will be derived two-sided and at a confidence probability of $1-\alpha=0.95$.

Listings

All recorded data will be listed by subject sorted by treatment group. Identification variables are centre number, participant number and treatment.

Derived data will be stored in special analysis data sets and will be calculated as outlined in section 6.1.

4.1 Conventions

4.1.1 Baseline definition

Results obtained on D1 (Screening/Randomization) of the study are considered as baseline results. In case of more than one result the closest to start of treatment will be used.

4.1.2 Missing data

In general, an observed cases approach will be applied in case of missing data, i.e., only the observed subject data at a given timepoint will be used.

There will be one notable exception to this rule for the primary efficacy endpoint: if a subject discontinued the study without a confirmed negative test result on D28 (and on any day in between), then the missing data will be imputed using a multiple imputation (MI) method, under the assumption that the results are missing at random (MAR). Details on the MI method can be found in section 4.6.1. The MI method will only be used for the primary efficacy endpoint.

Missing/incomplete information related to AEs and concomitant medications will be handled as listed below, when applicable. Following these steps using temporary programming will ensure that missing date imputation uses the most conservative approach.

In case of a (partially) missing onset date, and the end date is determined to be after the first date of study drug administration, the onset date will be imputed as follows:

• Partially missing onset date:

Statistical Analysis Plan	Version 1.0		Page 11 of 25
Sponsor	MedinCell	Protocol No	mdc-TTG-CT-002

- If the day part is missing and month is equal to month of first study drug administration, then day will be set to day part of first study drug administration date.
- o If the day part is missing and month is not equal to month of first study drug administration, then day will be set to the first day of that month.
- o If both day and month part are missing, and year is not the same as the year of the first study drug administration, then day and month will be set to 1 January.
- o If both day and month part are missing, and year is the same as the year of the first study drug administration, then day and month part will be set to day and month of first study drug administration.
- Complete missing onset date:
 - o If the end date is on or after date of first study drug administration, then the onset date will be set to the date of first study drug administration.
 - o If the end date is prior to the date of first study drug administration, then the onset date does not need an imputation, and the event or medication is considered a pre-treatment AE or prior medication.

In case of a (partially) missing end date, the end date will be imputed as follows:

- In case end date is partially missing:
 - o If the day part is missing, and the month and year present then day will be set to the last day of the month or the end of study date, whichever is earliest.
 - o If both day part and month part are missing and year is the same as the year of the end of study date, then day and month will be imputed with the end of study date.
 - o If both day part and month part are missing and year is prior to the year of end of study, then day and month will be set to 31 December.
- Completely missing end date:
 - o If the outcome of the AE is not marked as recovered/resolved:
 - The event will be assumed to be ongoing.
 - o If the outcome of the AE is marked as recovered/resolved:
 - The end date will be imputed with the end of study date.

In case both onset and end date are missing, the onset date will be imputed with the date of first study drug administration and the end date with the end of study date and the AE will be considered treatment emergent.

AEs with missing severity/relatedness will be considered severe/related.

Note that imputed dates will not be presented in the listings but will only be used in duration and onset time calculations, descriptive statistics and/or statistical analysis.

Statistical Analysis Plan	Version 1.0		Page 12 of 25
Sponsor	MedinCell	Protocol No	mdc-TTG-CT-002

[figure not shown]
For additional standards and conventions applied in the generation of statistical outputs please refer to section 8.

4.2 Demographic and other background data

4.2.1 Basic description

The disposition of subjects (cf. Section 3) will be tabulated by treatment and for the entire analysis set (pooled treatment groups). Frequencies of different reasons for exclusions (based on defined PD categories) from analysis sets will be listed.

Similarly, discontinued subjects will be described by frequencies of reason for termination and in individual listings.

The following background data will only be listed:

- Details on medical/surgery history
- Eligibility

4.2.2 Homogeneity tests

Homogeneity tests between treatment groups will be performed for age, sex, height, body weight and BMI.

4.3 IMP exposure, compliance

Treatment compliance will be described per visit by descriptive statistics on:

Statistical Analysis Plan	Version 1.0		Page 13 of 25
Sponsor	MedinCell	Protocol No	mdc-TTG-CT-002

- Number of participants with modified, interrupted or missed study treatment with reasons
- Number of missed doses
- Number of days without medication
- Number of tablets returned

4.4 Medical history

Medical history terms will be coded using the MedDRA dictionary, with version as documented in the Data Management Plan and presented descriptively by system organ class and preferred term. Details will be listed.

4.5 Prior and concomitant medication

"Concomitant" is defined as a medication which is taken during study treatment (starting before or during) and will be coded according to the WHO Drug Dictionary. Summary tables will be presented by international non-propriety name (INN) and WHO drug label.

Prior medication is defined as medication taken prior to the first dosing of study drug, i.e., the end date is before the first study drug intake.

Any medication with a missing start date will be considered 'concomitant', unless a (partial) end date shows that the medication is stopped prior to first study intake, then it will be considered as prior medication.

Medication with a missing end date will be considered continued during the study and should be considered as concomitant, unless a (partial) end date shows that the medication was stopped before the first study intake.

4.6 Efficacy

4.6.1 Primary endpoint

The primary endpoint is the proportion of laboratory-confirmed COVID-19 infections between baseline and Day 28. Frequency tables will be provided, and individual results will be listed.

For missing results of the primary endpoint, the multiple imputation (MI) method will be used. MI is performed using 3 general steps: imputation, analysis, and pooling. A total of 10 multiple imputations will be generated using a fully conditional specification (FCS) regression. This method conditions on observed values of the primary outcome measured at other time points (including baseline measurements) and possible other covariates that are related to the missing data pattern and/or primary endpoint. Furthermore, imputations will be performed in each treatment group separately and, if applicable, by stratification factor. The statistical model will be applied to each imputed dataset separately. The estimated parameters from the models will then be pooled using Rubin's combining rules. It should be noted that these combination rules rely on the assumption that the estimated

Statistical Analysis Plan	Version 1.0		Page 14 of 25
Sponsor	MedinCell	Protocol No	mdc-TTG-CT-002

statistics are approximately normally distributed, which may not be the case for the underlying data. Normalizing transformations will then be used on the estimated statistics prior to applying Rubin's rules.

The comparison between the two treatment groups of the proportion of participants will be performed using the Cochran Mantel Haenszel (CMH) chi-squared test. Odds-ratio, relative risk and risk differences and corresponding 95% CI will be reported. Country will be used as a stratification factor. In case the study was only performed in one country, the Chi-squared/Fisher's exact test will be used.

This analysis will be performed based on the mFAS and PP population using the planned treatment

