Terminology Criteria for Adverse Events (CTCAE version 5.0). **Statistical Methods:** Sample size: Sample size was calculated to compare the proportion of participants who become positive to SARS-CoV-2 RT-PCR within 1 month after randomisation between the two groups: Placebo group and experimental group receiving ivermectin up to D28. Based on a study assessing the transmission of SARS-CoV-2 infections in households carried out in the US between April and September 2020, the proportion of randomised participants becoming infected in the placebo group is estimated to be 54% (Grijalva et al, 2020).. A difference of 20% is expected between the two groups (OR=2.28). With a power of 90% (1- β) and a significance level of 5% (α), according to the Casagrande & Pike formula the required sample size to detect such difference with a test of comparison of two proportions is equal to 138 participants per arm (Casagrande et al, 1978). A total of 396 participants (198 per arm), rounded up to 400 participants (200 per arm) is required to account for the primary analysis. This sample size also accounts for an estimated dropout rate of 30%. Primary endpoint analysis: The comparison of proportion of participants who were tested positive for SARS-CoV-2 up to D28: placebo group versus ivermectin group, will be performed using the Cochran-Mantel Haenszel (CMH) chi-squared test at the two-sided 0.05 level. Twosided 95% confidence intervals (95% CI) for the proportion differences between groups will be provided. Odds-ratio and corresponding 95% CI will also be reported. The primary endpoint will also be analysed using a logistic regression with treatment group and country as a covariate. Moreover, the analysis of the primary endpoint will be performed for the PP population.

Clinical Protocol

Safety analysis:

Safety will be pooled analyses for the Safety set from all centres and countries. Placebo and ivermectin groups will be compared.

All adverse events (AEs) will be coded according to coding dictionaries (MedDRA, applicable version) and summarised at System Organ Class (SOC) and Preferred Term (PT) levels. AEs will be classified according to period of occurrence: pre-treatment AEs, treatment-emergent AEs (TEAEs) and post-treatment AEs (PTAEs). AE reporting will focus on TEAEs and PTAEs. Incidence of TEAEs and PTEAEs will be summarised and detailed by seriousness, intensity, action taken with the study medication, other action taken and relationship to study treatment.

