1.4 Planned sample size

The sample size was calculated to compare the proportion of participants who become positive to SARS-CoV-2 RT-PCR within 1 month after randomisation between the two groups: Placebo group and ivermectin group. The assumptions are based on results of a study assessing the transmission of SARS-CoV-2 infections in households carried out in the US between April and September 2020. Thus it is expected that the proportion of participants becoming infected in the placebo group is 54% or higher (Grijalva et al, 2020). Furthermore, a reduction by 20% is expected in the ivermectin group (OR=2.28).

When requiring a power of 90% (1- β) and a significance level of 5% (α), then according to the Casagrande & Pike formula the required sample size to detect such difference with a test of comparison of two proportions is equal to 138 participants per treatment arm (Casagrande et al, 1978).

A total of 396 participants (198 per arm), rounded up to 400 participants (200 per arm) is required to account for an estimated rate of randomised participants who won't be valued for the primary analysis of 30%.

[figure not shown]

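### Ten imputations for the primary endpoint leave avoidable Monte Carlo noise in the single primary p-value; at least 100 would remove most of it at almost no cost

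*SAP*

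**What the plan says.** SAP 4.1.2 uses observed cases in general and makes one exception. Participants who discontinue without a confirmed negative Day 28 result have the primary outcome imputed under missing at random, and "The MI method will only be used for the primary efficacy endpoint". Imputation is therefore the main handling of missing primary results, not a sensitivity analysis.

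SAP 4.6.1 gives the method: "A total of 10 multiple imputations will be generated using a fully conditional specification (FCS) regression". The model conditions on the outcome at other time points and possibly on other covariates, and "imputations will be performed in each treatment group separately and, if applicable, by stratification factor". Pooling is by Rubin's rules: "Normalizing transformations will then be used on the estimated statistics prior to applying" them. The transformation is not named.

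The primary comparison is the "Cochran-Mantel Haenszel (CMH) chi-squared test at the two-sided 0.05 level" (Protocol synopsis, Statistical Methods), stratified by country in the SAP. The primary set is the mFAS, with the per-protocol set as sensitivity analysis (SAP 3.5). SAP 1.4 raises 138 per arm to 198, rounded to 200, to "account for an estimated rate of randomised participants who" will not count in the primary analysis, put at 30%.

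The text available gives no reason for 10, no Monte Carlo error criterion and no rule for using more.

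**The concern.** Relative efficiency is the usual defence of a small number of imputations m. With a fraction of missing information γ it is 1/(1 + γ/m). For γ = 0.20 and m = 10 this is 1/1.02 = 98%. That figure describes the precision of the estimate over repeated trials. It does not say whether this trial's p-value would be the same under another seed.

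The trial rests on one primary test at 0.05. If the result lies close to that limit, the verdict can depend on the imputation draws as well as on the data. The chance is small, but it can be cut further by changing one number in the SAP.

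**Working it through.** **1. The plan's own figure.** Inputs are 54% vs 34%, two-sided 0.05, 90% power (SAP 1.4; Protocol synopsis).
- Uncorrected: n' = [1.960·√(2·0.44·0.56) + 1.282·√(0.54·0.46 + 0.34·0.66)]² / 0.20² = (1.376 + 0.881)² / 0.04 ≈ 127.4.
- Casagrande & Pike: n = (n'/4)·[1 + √(1 + 4/(n'·0.20))]² = 31.84·(1 + 1.0757)² ≈ 137.2, so 138 per arm.
- Allowance: 138/0.70 = 197.1, so 198 per arm.

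Both figures reproduce, so 138 per arm and 54% vs 34% are used below.

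**2. Assumption.** The missing fraction within the mFAS is not stated. It is set to 5%, 10% and 20%.

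**3. Hand calculation at 20% missing.** Take 44/110 vs 59/110 observed events, with 28 of 138 missing in each arm.
- Log odds ratio: ln(59/51) − ln(44/66) = 0.1457 + 0.4055 = 0.551.
- Observed-data variance: 1/59 + 1/51 + 1/44 + 1/66 = 0.0744, so z = 0.551/0.273 = 2.02 (p ≈ 0.043).
- Complete-data variance at 138 per arm: 1/(138·0.536·0.464) + 1/(138·0.40·0.60) ≈ 0.0593.
- Between-imputation variance: B ≈ 0.0744 − 0.0593 = 0.0151, so γ ≈ 0.0151/0.0744 = 0.20.
- The standard deviation of z over seeds is about √(γ/m): 0.142 for m = 10 and 0.045 for m = 100.
- m = 10: z = 2.02 ± 1.96·0.142, or 1.74 to 2.30, so p runs from about 0.021 to 0.082.
- m = 100: z = 2.02 ± 1.96·0.045, or 1.93 to 2.11, so p runs from about 0.035 to 0.053.

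This ignores the noise in B itself, which widens the range further when m = 10.

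**4. Simulation.** One borderline data set is held fixed for each missing fraction. Missing outcomes are imputed by arm (Beta posterior draw, then binomial). The log odds ratio is pooled by Rubin's rules with a t reference, and only the random draws are repeated (4,000 to 20,000 runs).

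| Missing | Observed events, ivermectin vs placebo | p for very large m | 95% range of p, m = 10 | Share p < 0.05, m = 10 | 95% range of p, m = 100 | Share p < 0.05, m = 100 |
|---|---|---|---|---|---|---|
| 5% | 56/131 vs 72/131 | 0.049 | 0.034-0.069 | 54% | 0.044-0.054 | 70% |
| 10% | 51/124 vs 67/124 | 0.042 | 0.025-0.072 | 70% | 0.036-0.050 | 97% |
| 20% | 44/110 vs 59/110 | 0.042 | 0.020-0.098 | 58% | 0.034-0.056 | 86% |

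The last digit moves by about 0.001 to 0.002 between runs. Counts are whole numbers, so the limiting p differs by row and the shares should not be compared down the columns. At 5% missing with 54/131 vs 71/131 (limiting p 0.036), 96% of seeds already give p < 0.05 with m = 10. With 198 per arm the m = 10 ranges are similar: 0.026-0.076 at 10% and 0.019-0.097 at 20%.

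**5. Risk over whole trials.** Chance that two seeds give different verdicts on the same trial, at 54% vs 34% and 138 per arm:

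| Missing | m = 10 | m = 100 |
|---|---|---|
| 5% | 1.5% | 0.5% |
| 10% | 2.5% | 0.4% |
| 20% | 4.5% | 1.5% |

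A repeat run at 20% gave 5.0% and 1.1%.

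**The case against.** **The 30% is not a missing-outcome rate.** A reader might infer from SAP 1.4 that 30% of primary outcomes will be imputed, and quote the m = 10 range for that case (0.016-0.123). The documents do not support this. The 30% covers all randomised participants who do not count in the primary analysis. SAP 3.3 and 3.4 drop those without a dose, without a post-randomisation efficacy assessment, or without a confirmed negative baseline PCR. They are excluded, not imputed. A participant with an earlier positive test is not missing either. So 30% is an upper bound at most, and this objection stands in full.

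**The planned model uses more information.** SAP 4.6.1 conditions on results at other time points, and PCR is scheduled on Days 4, 7 and 10. Suppose dropout occurs after Day 10 and 80% of infections are detected by then (neither is in the documents). With m = 10 the range at 20% missing becomes 0.025-0.062 (limiting p 0.039). At 10% missing it is 0.030-0.054, with 93% of seeds below 0.05. The ranges in the working are therefore near worst case. The noise shrinks but does not vanish, and early dropouts have few such results.

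**The simulated analysis is simpler than the planned one.** It pools an unstratified log odds ratio, not a country-stratified CMH statistic after an unnamed transformation. This limits the precision of the figures but not the mechanism.

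**Only borderline results are affected, and 100 is not a cure.** Both are true. With m = 100 the ranges for these data sets still reach 0.05.

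**The seed.** A reader might infer that no seed is specified. SAP section 4 refers to a section 6.1 that is not in the available text, so this cannot be concluded. A fixed seed would in any case prevent choosing among seeds without reducing Monte Carlo error.

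**Conclusion.** The point holds as a low-severity, free improvement. Ten imputations add Monte Carlo noise of about √(γ/10) to the primary z statistic, and 100 cut that by a factor of √10 ≈ 3.2. The gain is a fall of about 1 to 3 percentage points in the chance of a seed-dependent verdict at the planned effect, over 5 to 20% missing. The figures rest on that assumed missing fraction, 138 per arm, no auxiliary data and an unstratified log odds ratio.

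Two stronger readings are tempting. One is that 10 imputations is an error or makes the test invalid. It does not: Rubin's rules allow for finite m through the (1 + 1/m) term and the t reference, and nothing in the documents contradicts the choice. The other is that the trial's verdict is close to a coin toss. That describes only data sets picked to lie next to 0.05; a result well away from 0.05 does not change with the seed.

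**What to change.** In SAP 4.6.1:
- replace 10 with at least 100 imputations;
- state the random seed, set before unblinding, or point to where it is already stated;
- add a rule, also fixed before unblinding, that m is raised further if the Monte Carlo error of the primary p-value is not small relative to its distance from 0.05. At 20% missing, for example, m = 500 narrows the range in the working to 0.039-0.049.

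The cost is a few words in the SAP and seconds of computing on about 400 binary outcomes. No extra participants or data are needed, and the protocol text supplied does not mention a number of imputations. SAP 2.1 already allows a SAP amendment before database lock and unblinding.
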